ABSTRACT

TFE/translocation Renal Cell Carcinoma (tRCC) was formally recognized by the WHO in 2004 as a distinct, typically translocation-associated, RCC with characteristic morphology and strong nuclear immunohistochemical expression of transcription factor E3 (TFE3) or transcription factor Eb (TFEb). Cytogenetic translocations may include TFE3-ASPS, TFE3-PRCC, TFEb-alpha, or other variants. TFE3 and TFEb are members of the MiTF/TFE family of basic helix-loop-helix-leucine zipper transcription factors.¹⁻³ Nearly 50% of pediatric RCCs are tRCC, with a slight female predominance.⁴⁻⁶ tRCC presents in all races, and accounts for 1-5% of RCC overall, typically in adolescent and young adult ages.^{4, 7-11} This will be the first prospective therapeutic study dedicated to tRCC. Efficacy data for VEGFR TKI (axitinib) and PD1/PD-L1 targeted therapy (nivolumab), two key RCC therapeutic targets, will be assessed prospectively as single agents and in combination through a three-way randomization. As of Amendment 2A, Arm B is permanently closed to accrual and the study will proceed as a two-arm randomized trial assessing axitinib and nivolumab in combination or nivolumab alone. As of Amendment 5A, for those patients randomized to the nivolumab arm, cross-over to combination therapy will be permitted at disease progression. All patients treated with axitinib who, at the time, are < 18 years of age, will have pharmacokinetic assessments included.

Important biomarkers of response will be investigated and the biobanking of tissue for this rare cancer will occur. In addition, the behavior of tRCC will be comprehensively described across all ages. Baseline historical data, in combination with efficacy data from anti-angiogenic and immune checkpoint inhibitor therapy, will pave the way for continued future clinical investigation in this patient population.

EXPERIMENTAL DESIGN SCHEMA

1 cycle = 4 weeks.

* Absent disease progression or unacceptable toxicity. Tumor disease status imaging will be assessed after Cycles 2, 4, 6, 9, 12, and then every 4 cycles thereafter, or at any time clinical progression is suspected.

NOTE:

- Patients who have not had cytoreductive nephrectomy prior to trial enrollment but who elect to have cytoreductive nephrectomy during therapy may remain on protocol therapy.
- Cytoreductive nephrectomy is not permitted in the first 12 weeks after starting protocol therapy.
- Axitinib must be held for 7 days before and after surgery. See [Section 13.1.2](#) for more details.

1.0 GOALS AND OBJECTIVES (SCIENTIFIC AIMS)

1.1 Primary Aim

1.1.1 To establish the clinical activity, assessed primarily by progression-free survival, of nivolumab therapy with or without axitinib for advanced transcription factor E3/translocation morphology renal cell carcinoma (TFE/tRCC).

1.2 Secondary Aim

1.2.1 To further define the toxicities of the study arms in the treatment of translocation morphology RCC across all ages.

1.3 Exploratory Aims

1.3.1 To characterize tRCC clinical behavior across all age groups.

1.3.2 To evaluate type of antitumor immune response and stability of T cell activation before and after treatment with immunotherapy or antiangiogenic therapy.

1.3.3 To develop a tumor bank of tRCC tumor samples treated on study for further biological investigations.

1.3.4 To characterize the pharmacokinetics of axitinib when given in combination with nivolumab in pediatric patients with tRCC.

2.0 BACKGROUND

2.1 Introduction/Rationale for Development

Anti-vascular endothelial growth factor (anti-VEGF) receptor tyrosine kinase inhibitors and programmed death-1 (PD-1)/PD-1 ligand (PD-L1) inhibitors (anti-PD1) are either established treatment (anti-VEGF) or are being investigated (anti-PD1) for first-line treatment of patients with metastatic or unresectable renal cell carcinoma (RCC). Neither has been systematically investigated in a variant of RCC called TFE/tRCC.

TFE/tRCC was formally recognized by the WHO in 2004 as a distinct, typically translocation-associated, RCC with characteristic morphology and immunohistochemical expression of TFE3 or TFEb. Cytogenetic translocation partners to TFE3 may include TFE3-ASPS, TFE3-PRCC, TFEb-alpha, or other variants. Mechanisms for TFE upregulation are heterogeneous. TFE3 and TFEb are members of the MiTF/TFE family of basic helix-loop-helix zipper transcription factors.¹⁻³ Half of pediatric RCCs are tRCC, with a slight female predominance.⁴⁻⁶ tRCC occurs in all races, and accounts for 1-5% of RCC, typically in adolescents and young adults.^{4, 7-11}

The dominant presentation pattern for tRCC is one of advanced stage and rapid fatality, pointing to an aggressive cancer,¹²⁻¹⁵ though infrequent late recurrences^{13, 16} and prolonged stable disease^{4, 17, 18} point to an infrequently-occurring indolent pattern in a subset of patients. The import of positive lymph nodes, with rates of 41% in younger cohorts^{4, 5} and up to 50-80% in older tRCC cohorts,^{9, 10} is debated, with reports suggesting both favorable^{4, 11, 13, 19} and unfavorable outcomes.¹⁰ Nodal disease is also common with small primary tumors, with rates ranging from 20-33% for T1/T2 disease.^{5, 6, 11} Rates of hematogenous metastatic disease range from 9%^{5, 11} to 35-75% in select older tRCC cohorts.¹⁰ A meta-

analysis suggests that ASPS-TFE3 RCC is more likely to metastasize than PRCC-TFE3, but only older age or advanced stage, and not fusion subtype, was predictive of death.¹³ More recent reports from Korea and China respectively suggest that age > 45 years is an adverse prognostic factor¹², but neither Fuhrman grade nor WHO/ISUP grading is prognostic for tRCC.²⁰ Overall, in pediatric series, approximately 65% of tRCC cases present with the TNM classification system Stage 3 or 4 disease.⁵ For tRCC adult patient cohorts published by medical oncologists, referral patterns may have an impact on stage distribution since low-stage cases are not often referred by urologic oncologists.^{9,10}

Despite typical advance stage at presentation, often aggressive behavior, and apparent increasing awareness and diagnosis of tRCC, no formal treatment recommendations are available, as no dedicated adequately powered prospective therapeutic trials have been conducted. Biological targets of interest include c-Met,²¹⁻²³ VEGFR, mTOR,^{8, 24, 25} and PD1/PD-L1 immune checkpoint inhibition strategies.²⁶ Unfortunately, a phase 2 study of the c-MET inhibitor tivantinib did not produce responses in 6 tRCC patients treated, and more recent mTOR inhibitor trials (everolimus; ESPN trial) also failed to demonstrate any benefit in 7 tRCC patients treated.^{23, 27}

This will be the first prospective therapeutic study of tRCC to date, combining the resources of the Children's Oncology Group (COG) and other adult cooperative groups through the National Clinical Trials Network (NCTN). Efficacy data for vascular endothelial growth factor receptor (VEGFR) tyrosine kinase inhibitors (TKI) and programmed death-protein 1/programmed death-ligand 1 (PD1/PD-L1) targeted therapy, the two key RCC therapeutic targets, will be assessed prospectively for the first time specifically in tRCC, and the behavior of tRCC comprehensively described across all ages. Inter-group cooperation will be established for study of tRCC along with baseline historical data, and in combination with efficacy data from anti-angiogenic and immune checkpoint inhibitor therapy (as assessed by primary survival endpoints and secondary RECIST-based response metrics), pave the way for continued future clinical investigation in this patient population. Important biomarkers of response will be investigated and a disease-specific tissue bank of this rare cancer will be developed. In sum, this trial will provide the framework for establishing treatment guidelines for tRCC, based on biological and clinical interrogation.

2.1.1 VEGFR TKI in tRCC and Axitinib

VEGFR TKIs are approved by the US FDA for the treatment of clear cell RCC. Evidence of response of tRCCs to VEGFR TKIs is growing, with objective responses and rare durable complete remissions observed in both pediatric and adult patients.^{9, 24, 28-33} Malouf et al. reported the results of first-line therapy with sunitinib for tRCC; a median PFS of 8.2 months (n=11) vs. 2 months for cytokines (n=9) was achieved (log-rank p=0.003).²⁴ Unfortunately, the data from this report, which were extrapolated via retrospective reviews with varying selection criteria, have not been consistently reproduced. Choueiri et al. reported results from a retrospective review of 15 adult tRCC patients treated with anti-VEGF-based therapy (sunitinib [n=10], sorafenib [n=3], monoclonal anti-VEGF antibodies [n=2]) that demonstrated 3 objective responses (20%), 7 stable disease (47%), and 5 progressive disease (33%).⁹ Most recently, additional data regarding anti-VEGF based therapy in pediatric patients with tRCC demonstrated a PFS in the 5-8 month range.³⁴ Second generation more specific and potent VEGFR TKIs are demonstrating promising clinical benefit and diminished off-target effects.

Axitinib is a small molecule inhibitor of VEGFRs 1-3 that was FDA approved in January 2012 for advanced RCC after failure of one prior systemic therapy. Mechanistically, axitinib is a small molecule adenosine triphosphate (ATP)-competitive inhibitor that binds to the unphosphorylated “DFG-out” conformation of the catalytic domain of RTKs. The unique binding mode in the kinase domain affords its selectivity and relative high potency for VEGFRs 1-3 compared with sunitinib, pazopanib, sorafenib, and cediranib.^{35, 36}

2.1.2 PD1/PD-L1 in tRCC and Nivolumab

Recent reports of possibly improved durable response rates using immune checkpoint inhibitor therapy for RCC^{26, 37, 38} as compared with historical data using cytokine therapy, coupled with the FDA approval of several such inhibitors for other cancers,^{26, 39} have propelled PD1/PD-L1 immune checkpoint inhibitor therapy to the forefront of many RCC-based clinical investigations. The PD-L1 ligand is not expressed in normal kidney but is expressed in many RCC specimens, including 25-30% of tRCC.^{26, 40, 41} Specifically, Chang et al reported 25% (9/36) tRCC express PD-L1 which was associated with advanced stage and poor prognosis. Interestingly, PD-L1 tumor expression is associated with a worse clinical outcome in general, and shorter overall survival (OS) in RCC patients treated with anti-VEGF RTKIs.⁴²

2.1.3 Closure of Arm B: Axitinib monotherapy arm (Amendment 2A)

As of Amendment 2A, Arm B (the axitinib monotherapy arm) is closed to accrual of new patients. Enrollment challenges related to prohibiting prior anti-VEGF therapy and shifting community practice in favor of emphasizing PD1-targeted therapy in various carcinomas including renal cell carcinoma were key factors that led to the changes in Amendment 2A. Additional information has been recently published regarding the use of combination therapy with axitinib and PD-1/PD-L1 inhibitor compared to sunitinib in adults with advanced RCC.^{43, 44}

A key revision in Amendment 2A was to modify the eligibility criteria to permit patients who received one prior anti-VEGF agent to remain eligible for the study. As a result, Arm B (axitinib-only) becomes a less attractive treatment option, particularly for those patients who will have received prior anti-VEGF therapy, contributing to the closure of Arm B. Patients who were enrolled and assigned to Arm B prior to Amendment 2A will continue therapy on Arm B until off protocol therapy criteria is met.

2.2 **Adult Studies**

2.2.1 Axitinib

Axitinib, an FDA-approved anti-angiogenic therapy for second-line treatment of adult RCC, is the first VEGFR TKI to show superior activity when randomized against another VEGFR TKI (sorafenib) in a pivotal phase 3 RCC trial (AXIS trial), although tRCC was not studied.³⁵ Importantly, dose titration beyond 5 mg PO BID is feasible in some patients, and appeared to positively impact progression-free survival. Rini et al. recently reported a randomized phase 2 study of axitinib with or without dose titration in first-line metastatic RCC patients, demonstrating a survival advantage to dose titration (42.7 months vs. 30.4 months median survival).⁴⁵ In a prior study, Rini et al. reported that optimal axitinib exposure may differ among adult RCC patients, and that PK and blood pressure

could not be used to guide dosing.⁴⁶ Nonetheless, criteria for dose titration have included the following criteria for ≥ 2 consecutive weeks: BP $\leq 150/90$ mm Hg, no Grade 3/4 axitinib-related toxicities, no prior axitinib dose reductions, and use of no more than 2 concurrent antihypertensive medications.⁴⁵

2.2.2 Nivolumab in RCC

Motzer et al. published results of a phase 2 trial of the PD1 inhibitor nivolumab in metastatic RCC, demonstrating an objective response rate of 20%, 22%, and 20% and median OS of 18.2, 25.5, and 24.7 months for doses of 0.3, 2, and 10 mg/kg given intravenously every 3 weeks, respectively. Responses occurred more commonly in PD-L1 expressing tumors ($\geq 5\%$ PD-L1 expression) with overall response rate (ORR) of 31%, but the ORR of 18% for tumors expressing $< 5\%$ PD-L1 is still among the best ORRs in RCC. Median OS was not reached in the PD-L1 $\geq 5\%$ group and was 18.2 months in the PD-L1 $< 5\%$ group, the latter similar to that achieved with axitinib therapy in the second-line setting.³⁷ Some responding patients continued to respond for nearly a year after cessation of therapy.³⁸ Subsequently, results of the CheckMate 025 trial, where patients with advanced RCC previously treated with 1 or 2 regimens of antiangiogenic therapy were randomized to receive either nivolumab 3 mg/kg given q 2 weekly vs. everolimus 10 mg by mouth daily, were reported, demonstrating a median OS of 25 months with nivolumab and 19 months with everolimus. The ORR with nivolumab was 25% (vs. 5% with everolimus). Grade 3 and 4 events were less common with nivolumab (19%) than with everolimus (37%).³⁹

2.2.3 Anti-angiogenic plus PD1 Inhibitor Combination Trials

Studies combining anti-angiogenic therapies and PD1 inhibitors in RCC have recently been performed. A trial of nivolumab plus sunitinib confirmed that combining each agent at full dose was tolerable (nivolumab up to 5 mg/kg IV q 3 weekly; sunitinib 50 mg PO daily 4 weeks on/2 weeks off) and demonstrated objective anti-tumor activity (41% ORR by 6 weeks); however, hepatotoxicity was noted. Similarly, combining nivolumab with pazopanib resulted in increased toxicity, notably hepatotoxicity. Specifically, in trial NCT01472081, patients with mRCC (≥ 1 prior systemic therapy) received nivolumab in combination with sunitinib (50 mg, 4 weeks on/2 weeks off; Arm S) or pazopanib (800 mg daily; Arm P), until progression/unacceptable toxicity. The starting dose of nivolumab was 2 mg/kg IV Q3W (N2), with planned escalation to 5 mg/kg IV Q3W (N5). Based on tolerability, the Arm S N5 cohort was expanded to treatment-naïve patients. Primary objectives were safety/tolerability and determination of maximum tolerated dose (MTD) for the combinations; the secondary objective was antitumor activity (ORR and duration of response [DOR]). Seven patients were assigned to each of Arms S N2 and N5. No dose-limiting toxicities (DLTs) were observed and a MTD was not reached, thus N5 was expanded with 19 additional patients (total n=33). Arm P enrolled 20 patients at N2; 4 DLTs (elevated ALT/AST [n=3], fatigue [n=1]) were observed, leading to closure of this arm. Grade 3–4 related AEs were observed in 24/33 patients (73%) in Arm S and 12/20 patients (60%) in Arm P. The most common related Grade 3–4 AEs included elevated ALT (18%), hypertension and hyponatremia (15% each) in Arm S and elevated ALT/AST (20% each) and fatigue (15%) in Arm P. Hepatotoxicities were manageable using treatment algorithms. Grade 3 pneumonitis occurred in 1 patient (Arm S, N5). Grade 3–4 related AEs led to therapy discontinuation in 8/33 patients

(24%; 1 N2, 7 N5) in Arm S and 4/20 patients (20%) in Arm P. ORR was 52% (17/33) in Arm S and 45% (9/20) in Arm P. Responses occurred by first assessment (6 wks) in 41% (Arm S) and 56% (Arm P) of responding patients and were durable (range: Arm S: 12.1+ to 54 wks; Arm P: 12.1 to 69.1+ wks). Stable disease rate was 33% (n=11) in Arm S and 35% (n=7) in Arm P. PFS rate at 24 wks was 78% for Arm S and 55% for Arm P. The authors concluded that nivolumab plus sunitinib or pazopanib showed encouraging antitumor activity and a manageable safety profile in patients with mRCC.⁴²

Axitinib has been combined with a PD1 inhibitor (pembrolizumab) in RCC (NCT02133742) and proven tolerable when each agent is administered at its independent MTD/RP2D.^{47, 48}

2.3 Pediatric Studies

There have been no combination data for axitinib and nivolumab in children. The Children's Oncology Group has completed accrual to study ADVL1315 ([NCT02164838](#)), a phase 1 study of axitinib in pediatric solid tumor patients with relapsed or refractory disease. Oral axitinib tablets were administered BID, continuously in 28-day cycles. Dose Levels 2.4 and 3.2 mg/m²/dose were evaluated using a rolling 6 design. Serial PK were obtained in Cycle 1. Eighteen patients were enrolled with 1 ineligible (inadequate time from prior therapy). The median age was 13.5 years (range: 5-17 years); 10 were male. Patients received a median 3 prior chemotherapy regimens (range: 1-8). Cancer diagnoses included soft tissue sarcomas (n=7), Ewing (n=3) and osteosarcoma (n=1), neuroblastoma (n=2), Wilms tumor (n=1), hepatoblastoma (n=1), hepatocellular carcinoma (n=1), medullary carcinoma (n=1), and epithelial-myoepithelial carcinoma (n=1). Toxicity data are available for 15 patients (6 patients at Dose Level 1; 5 patients at Dose Level 2, and 4 patients on an expanded PK cohort). Two patients were inevaluable for toxicity due to inadequate drug exposure. DLTs occurred in 0/6 and 2/5 patients treated at Dose Levels 1 and 2, respectively (palmar-plantar erythrodysesthesia syndrome [1]; intratumoral hemorrhage [1]). Cycle 1 hematologic toxicities included Grade 3 lymphopenia (1) and Grade 1 or 2 anemia (4), lymphopenia (3), elevated hemoglobin (3), leukopenia (2), neutropenia (1), thrombocytopenia (1), and lymphocytosis (1). Non-hematologic toxicities included Grade 1 or 2 nausea (5), hypertension (4), anorexia (3), creatinine elevation (2), diarrhea (2), fatigue (2), headache (2), lipase elevation (2), proteinuria (2), and acneiform rash (2). The most common subsequent cycle Grade 3 or 4 toxicities included neutropenia (Grade 3 [3], Grade 4 [1]) and lymphopenia (Grade 3 [1], Grade 4 [1]). Authors concluded that axitinib is tolerated in pediatric patients. The MTD of axitinib given to children with solid tumors is 2.4 mg/m²/dose, corresponding to 4 mg BID (or 80%) of the adult dose.⁴⁹ PK analysis demonstrated peak plasma concentrations 2 h after dose with an average half-life of 0.9 to 5.2 h. There was substantial variability in exposure that appeared to be dose dependent and unexpected accumulation ranging from 0.27- to 4.74-fold. AUC exposures at the pediatric MTD were at levels predicted to be active in adult RCC trials.⁴⁹

In ADVL1315, sixteen patients were evaluable for response; 15 patients had sufficient evaluations to report a response (1 patient did not have all required evaluations obtained). One patient with alveolar soft part sarcoma (also known to be a TFE3 driven cancer) had a confirmed partial response that was durable for 6 months prior to clinical progression of disease and discontinuation of protocol therapy. Five patients had stable disease for up to 6 cycles including 2 patients with osteosarcoma and 1 each with malignant peripheral nerve sheath tumor, Ewing sarcoma, and hepatocellular carcinoma.⁴⁹

COG study ADVL1412 ([NCT02304458](#)), *A Phase 1/2 Study of Nivolumab (IND# [REDACTED]) in Children, Adolescents, and Young Adults with Recurrent or Refractory Solid Tumors as a Single Agent in Combination with Ipilimumab*, is closed to accrual. Full dose therapy analogous to adult trials dosing was confirmed tolerable. (COG ADVL1412 study report)

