ORR: A logistic regression model for overall response, stratified by the stratification factors used at randomization (age and prior therapy) will be fit, including treatment arm as a key covariate. From this model, the odds ratio for treatment arm will be reported with a 70% confidence interval. The ORR observed within each treatment arm will also be reported.

OS: A stratified, one-sided log-rank test (using the stratification factors at randomization, age and prior therapy) will be performed to compare treatment arms with alpha = 0.15. Cox proportional hazards models will also be fit to evaluate the final hazard ratio between the treatment arms, with exploratory modeling taking into account the potential influence of other factors (e.g., baseline disease burden, upfront vs. delayed nephrectomy). From these models, the hazard ratio for treatment assignment will be reported with a 70% confidence interval (to align with the overall alpha level of the primary log-rank test).

AEs: All Grade 3 or higher non-hematologic toxicities and all Grade 4-5 adverse events occurring during protocol therapy or within 100 days of treatment discontinuation, including crossover for patients who receive crossover combination therapy, will be analyzed. The rates of these events will be reported separately by treatment arm (including crossover as a “3rd” arm for this purpose), and both by individual AE and class of AE (e.g., hematologic). Given that some AEs may be rare, Fisher Exact tests will be used to test for statistical significance among any apparent differences by treatment arm.

Exploratory Analyses

Exploratory Aim 1.3.1: To characterize tRCC clinical behavior across all age groups.
We will list and summarize the frequency of site(s) of disease at presentation (including extent of lymph node involvement), site(s) of relapse, surgical practices on protocol therapy, and radiotherapy practices on protocol therapy. We will also summarize the overall response rate (ORR) submitted by the enrolling institution.

Exploratory Aim 1.3.2: To evaluate type of antitumor immune response and stability of T cell activation before and after treatment with immunotherapy or antiangiogenic therapy.

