9.5 Monitoring Boundary for Dose-Limiting Toxicities

Definitions of DLTs provided in ADVL1315 (for axitinib related DLTs) and ADVL1412 (for PD1-targeting immune checkpoint DLTs) will be used ([Section 5.1](#)). DLTs in each arm will be monitored at least weekly to ensure there is no excess toxicity, specifically. No

more than 3 patients (in the first 10 patients treated) experiencing protocol-defined DLTs during the first cycle (4 weeks) of treatment, and no more than 30% of patients experiencing protocol-defined DLTs during the first cycle (4 weeks) of treatment thereafter. Excess toxicities in the combination arm will lead to temporary suspension of accrual so discontinuation or dose reduction may be considered via a formal amendment.

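### DLT monitoring and AE reporting pool children with adults, so a high toxicity rate in a paediatric minority can stay inside the Section 9.5 limit and out of the planned tables

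*Combined protocol and SAP*

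**What the plan says.** - **Evidence in children.** Section 2.3 states: "There have been no combination data for axitinib and nivolumab in children". Its axitinib data in children are single-agent: "DLTs occurred in 0/6 and 2/5 patients treated at Dose Levels 1 and 2, respectively". Section 2.3 also cites a separate paediatric nivolumab study that found full-dose therapy tolerable.
- **Aim.** The secondary aim (Section 1.2) is: "To further define the toxicities of the study arms in the treatment of translocation morphology RCC across all ages".
- **Age elsewhere in the plan.** Section 4.1 sets axitinib and nivolumab doses separately below and above 18 years. Section 9.2 stratifies randomisation at 18 years.
- **Boundary.** Section 9.5 works by arm and rules out "more than 3 patients (in the first 10 patients treated) experiencing protocol-defined DLTs during the first cycle (4 weeks) of treatment". So a third DLT is tolerated in that opening group and a fourth crosses the limit. For later patients the ceiling is a proportion, 30%, again counting Cycle 1 events only. If the combination arm goes over, accrual is paused while an amendment is considered. Age is not mentioned.
- **AE analysis.** Section 9.3: "The rates of these events will be reported separately by treatment arm", with crossover patients as a third group, by individual AE and AE class, and with Fisher exact tests between arms. Age is not mentioned here either.
- **Other routes.** Section 5.1 asks that the Study Chair be told of any suspected or confirmed DLT. Section 12.2 requires unexpected frequencies of serious events to go to the DSMC.

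**The concern.** Children have the least prior information on this combination, and the protocol treats them separately for dosing, randomisation and pharmacokinetics. It does not do so for toxicity. A boundary on the pooled count responds to the average of two rates. If children are a minority and tolerate the combination worse than adults, that average can stay at or below 30% while the paediatric rate is far above it.

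Two things are at stake. Accrual of children to Arm A could continue above the protocol's own limit with no numeric trigger reached. And the planned final tables would not show whether toxicity differed by age, which the secondary aim needs.

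**Working it through.** **The plan's own figure.** The two parts of the Section 9.5 limit agree: 3/10 = 30%. The plan states no crossing probabilities, so there are none to reproduce.

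**Inputs from the documents.** At most 3 DLTs in the first 10 treated, so the limit is crossed at 4 or more; then at most 30% (Section 9.5). Target 28 patients at 1:1 (Section 9.2), so 28/2 = 14 in Arm A.

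**Assumptions.** The number of children and the adult DLT rate are not given, so both are varied. The paediatric rate is set at 60%, which is 2 × 30%; this is a hypothetical value. The first 10 are read as 10 per arm. Crossover patients are left out, because Section 9.5 does not say whether they count.

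**Literal application.** 4 children with 3 DLTs plus 6 adults with 0 gives 3/10 = 30%: not crossed. The rate in the children is 3/4 = 75%.

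**Crossing probability at the first 10.** With k children, the total is Binomial(k, 0.60) + Binomial(10 − k, a), where a is the adult rate, and P(crossed) = 1 − P(total ≤ 3). For k = 4 and a = 0.10:

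- P(0) = 0.4⁴ × 0.9⁶ = 0.0136
- P(1) = 0.0907, P(2) = 0.2406, P(3) = 0.3216
- P(crossed) = 1 − 0.6665 = 0.333

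| Children in first 10 | Adults 5% | Adults 10% | Adults 20% | Adults 30% |
|---|---|---|---|---|
| 3 | 8.5% | 18.5% | 39.8% | 59.8% |
| 4 | 23.3% | 33.3% | 51.9% | 67.6% |
| 5 | 42.0% | 49.8% | 63.4% | 74.6% |
| 8 | 83.9% | 85.0% | 87.3% | 89.3% |

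If all 10 patients had a 60% rate, the limit would be crossed 94.5% of the time.

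**Where dilution hides the signal on average.** With a fraction f of children, the expected pooled rate is 0.60f + a(1 − f). It stays at or below 30% while f ≤ (0.30 − a)/(0.60 − a). That is 0.20/0.50 = 40% for a = 10%, and 0.10/0.40 = 25% for a = 20%.

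**Full rule over 14 Arm A patients.** By simulation, with each patient a child with probability 20% to 40% and children at 60%, the rule is crossed in 25% to 58% of trials with adults at 10%, and in 52% to 75% with adults at 20%.

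**Illustrative paediatric trigger.** Suppose a pause also followed 2 or more DLTs in the first 5 children, or more than 30% of children after that. With children at 60%, this alone is crossed in 51% to 88% of the same trials. Its cost, as the chance of any pause when both age groups have the same rate (14 in Arm A, 20% to 40% children):

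| DLT rate in both groups | Pooled rule alone | Pooled plus paediatric |
|---|---|---|
| 15% | about 12% | about 15% to 23% |
| 20% | about 25% | about 30% to 38% |

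**The case against.** **The rates are assumed.** A sixfold gap (60% against 10%) is not in the documents. The adult DLT counts that Section 2.2.3 gives for nivolumab with an anti-VEGF agent are none with sunitinib and 4 in 20 (20%) with pazopanib. At 20% in adults, the pooled rule does appreciably better. If most early Arm A patients are children, the problem largely disappears; Section 2.1 describes the disease as typical of adolescents and young adults. This stands, and it is why the result is given as a range.

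**A reader might infer that a paediatric signal would trigger nothing.** The documents do not support that. DLTs are reviewed at least weekly, the Study Chair is notified of each, and DSMC referral of unexpected frequencies is an obligation. Section 4.3.2 gives children weekly examinations and blood counts in Cycle 1, against every other week for adults. Three DLTs in four children would be seen. What is missing is a numeric or age-specific threshold and a planned tabulation.

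**A reader might infer that adults have data on this exact combination.** They do not in these documents. The adult evidence cited is nivolumab with sunitinib or pazopanib, and axitinib with other PD-1/PD-L1 inhibitors (Sections 2.1.3 and 2.2.3).

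**A reader might take the 2/5 as a warning about the starting dose.** Those DLTs were at Dose Level 2 of the phase 1 study (3.2 mg/m²/dose). The starting dose here is 2.4 mg/m²/dose, where the count was 0/6.

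**A separate paediatric boundary is a trade-off.** With few children it raises false pauses, as the last table shows. This stands, so a specific threshold is not put forward as a correction.

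**Conclusion.** The point holds as a gap in planned monitoring and reporting. Neither Section 9.5 nor the AE paragraph of Section 9.3 separates patients under 18, although the protocol's aim, dosing and randomisation all do, and it has no paediatric data for the combination.

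The size is conditional. A paediatric DLT rate at twice the limit is likely to escape the pooled boundary at the first 10 when children are up to half of them and adults are near 10%: it is missed in about 50% to 82% of trials with 3 to 5 children. With adults at 20% the miss rate is 37% to 60%. With 8 children in 10 it is about 15% or less for adult rates of 10% or more. The reporting gap needs no assumption: as planned, the AE results need not show children separately. The documents do not establish that children have a higher DLT rate, or that a particular paediatric limit is required.

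**What to change.** 1. **Section 9.3.** Report the planned AE rates, and first-cycle DLT rates, by arm within the two age strata used at randomisation. DLTs need their own line because Section 5.1 counts some Grade 2 events that the Section 9.3 AE set leaves out; Section 11.10 already collects all DLTs. Stratify the Arm A versus Arm C comparison by age, for example with an exact stratified test. Treat within-stratum rates as descriptive, with exact intervals.
2. **Section 9.5.** Keep the pooled boundary. At each existing review, tabulate the Arm A DLT count and denominator for patients under 18 separately, and pass it to the DSMC. State whether crossover patients are counted.
3. **Numeric paediatric trigger.** Leave the choice, and any level, to the sponsor and DSMC, with operating characteristics stated over a range of paediatric shares and adult rates.

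**Cost.** Items 1 and 2 need a few sentences and no new data. The downside is small cells: 3 of 4 has an exact 95% interval of about 19% to 99%, so the strata will describe rather than test. Item 3 has a real cost in extra pauses, shown in the working, and should be weighed before adoption.
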